1.1.3 Afatinib Safety Profile

A **Comprehensive Adverse Events and Potential Risks (CAEPR)** list using NCI Common Terminology Criteria for Adverse Events (CTCAE) terms is included in Section [3.3](#) of the protocol.

Based on phase I studies, the MTD for continuous administration of single agent oral afatinib was 50mg or 40mg daily. The data from the monotherapy trials indicate that the safety profile of afatinib is characterized by significant incidence of dose-dependent gastrointestinal and skin toxicities. The most common toxicities seen are: diarrhea, rash/acne and stomatitis. The majority of these are low grade (grade 1-2).

AEs of special interest

Diarrhea, rash, stomatitis and ILD are considered AEs of special interest because they are either known class effects (*i.e.*, have been observed with other EGFR inhibitors) or are potentially life-threatening (Investigator's Brochure, 2014). The following sections provide integrated summaries for these AEs across different clinical trials, with emphasis on trials using afatinib as monotherapy, especially at the RP2D.

Section [3.4](#) of the protocol has dose modification guidelines for toxicities.

Diarrhea

Diarrhea is the most common AE observed across afatinib monotherapy trials, typically affecting > 80% of patients. Grade 3 diarrhea with the 40mg po qd dose was 15.3% vs 17.2% with the 50mg po qd dose. The majority of patients (> 70%) experienced diarrhea within 14 days of starting afatinib. Grade 3 diarrhea most frequently occurred within the first 6 weeks of treatment. Risk factors for grade 3 diarrhea included: low body weight (< 50kg), females, and low baseline renal function (CrCl < 80mL/min). SAE of diarrhea were reported in 4-7% of patients and grade 5 diarrhea has been reported. Dehydration and renal impairment have both been reported related to diarrhea. Proactive management of diarrhea including adequate hydration and antidiarrheal agents (i.e. loperamide) is important and should be started at first signs of diarrhea.

Rash/Acne

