Rash/acne is one of the most common AE reported in patients on afatinib trials with the total incidence reaching 90% in the pivotal NSCLC trial using afatinib monotherapy at 40mg po qd. Grade 3 rash/acne was similar at 40mg and 50mg (14 and 16.2%, respectively). In general, rash manifests as a mild or moderate erythematous and acneiform rash, which may occur or worsen in areas exposed to sun. The majority of patients experienced onset of rash/acne within the first 4 weeks of treatment (79.7% at 40mg and 65.1% at 50mg). Risk factors for grade 3 events included low body weight (< 50kg) and low baseline renal function(<80mL/min). Protective clothing, and/or use of sun screen is advisable. Early intervention (e.g. emollients, antibiotics) of dermatologic reaction is also recommended. Dose reduction allowed successful management of rash in the majority of cases. Rare cases of bullous, blistering and exfoliative skin conditions have been reported including cases suggestive of Stevens-Johnson syndrome. Afatinib should be interrupted or discontinued if these occur.

Palmar-plantar erythrodysesthesia syndrome was also reported as a dermatologic AE with afatinib at rates of 6.6-7.7%. The majority were grade 1-2, but grade 3 events have been reported.

Interstitial Lung disease (ILD)

ILD or ILD-like events are a well-described, infrequent risk of EGFR inhibitors. There have been reports of ILD or ILD-like events in 1.5% of afatinib treated patients. The rate of these events is similar to that observed with other EGFR inhibitors. Careful assessment of all patients with an acute onset and/or unexplained worsening of pulmonary symptoms (dyspnea, cough, fever) should be performed to exclude ILD. Treatment should be interrupted pending investigation of these symptoms. If ILD is diagnosed, afatinib should be permanently discontinued and appropriate treatment instituted as necessary.

Hepatic Adverse Events

Hepatic AEs include elevated hepatic enzymes, which are primarily grade 1-2 and did not lead to treatment discontinuation. In the entire afatinib exposed population, 10.8% (95% CI 10.1-11.7%) were reported with AEs indicative of hepatic impairment with 8 pts with hepatic AEs leading to death. These were considered not related to afatinib in 5 patients (related to progressive disease or sepsis). Drug-related fatal case of acute hepatic failure has been reported. Periodic liver function testing is recommended in patients treated with afatinib.

Keratitis

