3.4 Dose Modifications

All toxicity grades below are described using the NCI Common Terminology Criteria for Adverse Events (CTCAE) version 4.0.

All appropriate treatment areas should have access to a copy of the CTCAE version 4.0. A copy of the CTCAE version 4.0 can be downloaded from the CTEP website (<http://ctep.cancer.gov>).

Afatinib will be administered at the recommended dose of 40 mg orally once daily starting on the first day of administration and continue until disease progression or unacceptable toxicity. We chose the 40 mg daily dose since the Css still remains adequate at this dose. With the 50 mg dose used in previous trials of afatinib in HER2+, patients showed poor tolerability data. High Rates of dose modification were seen in previous studies with 50 mg daily dosing.

Afatinib will not be held for hematologic toxicity, unless it is determined to be a drug-related grade 3 or 4 hematologic event.

Treatment may be delayed by 2 weeks due to toxicity. If treatment is delayed beyond 2 weeks the subject will come off study for unacceptable toxicity.

Discontinuation of afatinib for any reason for longer than 2 weeks will result in removal of the patient from this subprotocol.

The afatinib dose may be adjusted according to individual patient tolerance as outlined below.

Table 1. Dose Levels for Afatinib

Dose Level	Daily Dose/ Route	Dispensed As	Schedule
Starting dose level: 0	40 mg, PO	1 × 40-mg tablet	Daily during 4-week cycle
-1	30 mg, PO	1 × 30 mg tablet	Daily during 4-week cycle
-2	20 mg, PO	1 × 20-mg tablet	Daily during 4-week cycle

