3.4.2 Toxicity monitoring & dose modification

Patients will have clinical and laboratory assessment while on study as per the Study Calendar. No dose escalations of afatinib will be permitted.

In the event of any CTC, version 4.0 drug-related grade 3 or 4 non-hematologic adverse event(s), drug should be held until the toxicity resolves to ≤ grade 1 and then the drug should be restarted at a one dose-level reduction with the exception noted in table 2. In addition, no dose modifications will be needed for low electrolytes (Na, K, Phos, Mg) unless the grade 3 or 4 adverse event were to last >48

hours despite optimal electrolyte repletion. Please see supportive care guidelines for nausea, vomiting, diarrhea, fatigue, and rash.

Patients should be carefully monitored for clinical signs and symptoms of CHF while receiving afatinib. In the presence of clinical manifestations of CHF, discontinuation of afatinib and assessment of LVEF is recommended.

In the event of any CTC, version 4.0 drug-related grade 3 or 4 hematologic adverse event(s), the drug should be held until the toxicity resolves to \leq grade 1 and then the drug should be restarted at a one dose-level reduction.

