Rash (Papulopustular, pustular, acneiform, maculo-papular) ^d	Continue at the same dose level.	Continue at the same dose level unless rash persists and is intolerable or worsens over > 7 days. If this occurs: Withhold dose until toxicity is grade ≤ 1 . Then reduce dose by 1 level and resume treatment.	Withhold dose until toxicity is grade ≤ 1 . Then reduce dose by 1 level and resume treatment.	Discontinue study treatment
Drug-induced hepatic impairment	Continue at the same dose level.	Continue at the same dose level.	Withhold dose until toxicity is grade ≤ 1 or has returned to baseline. Then reduce the dose by 1 level and resume treatment.	Discontinue study treatment

Ulcerative keratitis	Continue at the same dose level.	Continue at the same dose level.	Withhold dose until toxicity is grade ≤ 1 or has returned to baseline. Then reduce the dose by 1 level and resume treatment.	Discontinue study treatment
Interstitial Lung Disease	If a patient develops respiratory problems consistent with possible interstitial lung disease (ILD), afatinib is to be withheld pending a diagnostic evaluation. Afatinib will be discontinued if a diagnosis of ILD is confirmed.			

- a. *No dose modifications will be needed for low electrolytes (Na, K, Phos, Mg) unless the grade 3 or 4 adverse event were to last >48 hours despite optimal electrolyte repletion*
- b. *See supportive care for diarrhea in Section [3.5.1](#)*
- c. *Nausea and vomiting should be graded after maximal medical management*
- d. *See supportive care for rash in Section [3.5.1](#)*

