treatment) may be added at investigator's discretion.

Systemic and topical treatment should be initiated at the start of CTCAE Grade 2 rash and continued until improvement or resolution to CTCAE Grade ≤ 1 . If grade 2 rash persists for ≥ 7 days despite treatment and is poorly tolerated by the patient, the investigator may choose to pause treatment for up to 14 days followed by a reduction in the dose of afatinib according to the dose reduction scheme in Table 2.

Management of Fatigue

For intolerable fatigue (grade ≥ 3), the next cycle of treatment may be delayed by up to two weeks.

Management of Interstitial Lung Disease

Although quite rare, interstitial lung disease (ILD) is a class effect of EGFR TKIs and can be life threatening. Therefore, patients should be monitored closely for symptoms consistent with ILD, such as new onset dyspnea without an obvious cause. Chest CT should be obtained to look for interstitial fibrotic changes if ILD is suspected. In the event that ILD is suspected, drug treatment should be discontinued and the patient should receive appropriate medical management and supportive care. Although there is no established treatment, systemic corticosteroids are often administered. Afatinib should not be restarted in those patients suspected of having drug-related ILD and the subject should be removed from the study.

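### Section 3.5.1 bars restarting afatinib on suspicion of drug-related ILD, while Table 2 ties permanent discontinuation to a confirmed diagnosis, so an inconclusive work-up is handled differently by the two texts

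*Protocol*

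**What the plan says.** Three places in the protocol deal with possible ILD.

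- **Section 3.5.1, Management of Interstitial Lung Disease.** On suspicion it calls for imaging ("Chest CT should be obtained to look for interstitial fibrotic changes if ILD is suspected") and for stopping drug ("In the event that ILD is suspected, drug treatment should be discontinued"). It then adds: "Afatinib should not be restarted in those patients suspected of having drug-related ILD and the subject should be removed from the study". Neither restart nor removal is made to depend on what the CT shows.
- **Section 3.4.3, Table 2, ILD row.** For respiratory symptoms that could be ILD, "afatinib is to be withheld pending a diagnostic evaluation. Afatinib will be discontinued if a diagnosis of ILD is confirmed". The row does not say what follows if ILD is excluded or if the evaluation settles nothing.
- **Section 1.1.3, background on ILD.** "Treatment should be interrupted pending investigation of these symptoms. If ILD is diagnosed, afatinib should be permanently discontinued". This has the same structure as Table 2.

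A general limit in Section 3.4 also applies: "Discontinuation of afatinib for any reason for longer than 2 weeks will result in removal of the patient from this subprotocol".

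Two pointers bear on which text a site would consult first. Section 1.1.3 tells the reader that Section 3.4 "of the protocol has dose modification guidelines for toxicities". Section 3.4.2 refers to the supportive care text for a list of toxicities that does not include ILD: "Please see supportive care guidelines for nausea, vomiting, diarrhea, fatigue, and rash".

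**The concern.** Whether a patient may receive afatinib again turns on suspicion in one text and on confirmation in the other. The protocol treats ILD as an adverse event of special interest, and Section 3.5.1 describes it as potentially life threatening, so the re-exposure rule ought to read the same wherever a site looks it up.

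The error can run in either direction. After an inconclusive work-up, a site working from Table 2 could resume drug that Section 3.5.1 forbids. After a negative work-up, a site that applies Section 3.5.1 to anyone who was ever suspected would take off study a patient whom Table 2 seems to let continue.

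Unconfirmed suspicion is foreseeable. Section 1.1.3 gives dyspnea, cough and fever as the symptoms that should prompt an assessment, and the CAEPR in Section 3.3 lists all three separately as possibly related to afatinib. The symptoms that start the work-up are therefore not specific to ILD.

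**Working it through.** The protocol states no figure on this point, so the check sets the texts side by side for each way a work-up can end.

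| Result of work-up | Section 3.5.1 | Table 2, ILD row | Same outcome? |
|---|---|---|---|
| Drug-related ILD confirmed, within 2 weeks | No restart, off study | Discontinue | Yes: drug stops for good |
| Inconclusive, completed within 2 weeks | Still suspected: no restart, off study | Not confirmed: discontinuation not required, resumption implied | **No** |
| ILD excluded, within 2 weeks | Depends on how suspicion is read (below) | Discontinuation not required, resumption implied | Only on one reading of Section 3.5.1 |
| Drug held longer than 2 weeks | Off | Off, under the general limit in Section 3.4 | Yes |

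**Common ground.** Every text stops drug as soon as ILD is suspected. Every text stops it permanently once drug-related ILD is confirmed.

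**Inconclusive work-up.** Suppose Section 3.5.1 is read narrowly, so that its restart bar covers only patients still suspected of drug-related ILD after the evaluation. A patient whose work-up has ended without an answer is still in that group and may not restart. The same patient does not have a confirmed diagnosis, so Table 2's stated condition for discontinuation is not met, and the evaluation for which drug was held is over. The divergence therefore does not depend on a strained reading of Section 3.5.1.

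**ILD excluded.** On the narrow reading the suspicion has been lifted, the bar no longer applies and the texts agree. They part only if having been suspected is enough whatever the CT shows. The wording allows this second reading, because nothing in Section 3.5.1 is conditional on the result, but it is the less natural one.

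**Which text prevails.** The pointer to Section 3.4 and the omission of ILD from the supportive-care list both favour Table 2. Against that, Section 3.5.1 is written as an instruction and includes a consequence, removal from study, that the Table 2 row does not mention. No clause in this document ranks the two.

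**Scale only.** Inputs: 1.5% of afatinib-treated patients with ILD or ILD-like events (Section 1.1.3), and an accrual goal of 70 (Schema).

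- Expected events: n × p = 70 × 0.015 = 1.05.
- Chance of at least one: 1 − (1 − p)^n = 1 − 0.985^70 ≈ 0.65.

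This assumes that the 1.5% carries over to this population. It counts reported events, not suspected cases that were never confirmed, and those are the cases where the texts diverge. The document gives no rate for them.

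**The case against.** The strongest reply is that a site can obey both texts at once. Table 2 makes confirmation a sufficient reason to discontinue and does not say it is the only one, so a stricter rule elsewhere adds to it without contradicting it. The other Table 2 rows that withhold drug say what happens next, usually a reduction by one level and resumption; the ILD row has no such clause. An inconclusive evaluation could also be regarded as still pending, in which case drug stays on hold until the 2-week limit removes the patient. On this view the only explicit restart rule is the one in Section 3.5.1, and it is the safe one.

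Much of this stands. A reader might infer that Table 2 permits restart whenever ILD is unconfirmed. The document does not say so; permission is only implied by a hold that lasts until evaluation. A reader might also infer that the texts conflict for every patient who is cleared. That does not follow either. The restart bar is limited to suspicion of *drug-related* ILD, and Section 3.4 speaks of discontinuations lasting more than 2 weeks, which implies that shorter ones exist. Stopping drug on suspicion in Section 3.5.1 therefore need not be permanent.

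What does not stand is the claim that nothing is left to resolve. An evaluation can be finished and still be indeterminate. When that happens within 2 weeks, one text forbids restart and the other leaves it open. The stricter outcome follows only if the site happens to consult Section 3.5.1, although both pointers lead towards Section 3.4.

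The Master Protocol is not among the documents at hand, so the absence of a ranking clause is established for this subprotocol only.

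**Conclusion.** The point holds for one clearly defined situation: a work-up for possible ILD that is completed within 2 weeks and neither confirms nor excludes drug-related ILD. For work-ups that exclude ILD, the divergence is conditional on reading suspicion in Section 3.5.1 as applying regardless of the result. For confirmed drug-related ILD, and for holds beyond 2 weeks, there is no divergence.

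This is a minor harmonisation of a safety rule, worth making because it governs re-exposure after a potentially life-threatening toxicity. The number of patients affected cannot be calculated from the document.

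A reader might infer that differing removals would disturb the trial's results. The documents give no basis for that: no endpoint, sample size or analysis figure depends on this wording.

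The conclusion rests on two assumptions: that an inconclusive evaluation counts as completed, not as indefinitely pending, and that no clause in the Master Protocol already ranks the two texts.

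**What to change.** Use the same wording in the ILD paragraph of Section 3.5.1 and in the ILD row of Table 2:

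> *Withhold afatinib when ILD is suspected, pending diagnostic evaluation including chest CT. Permanently discontinue if ILD is confirmed or if drug-related ILD cannot be excluded. If ILD is excluded within 2 weeks, afatinib may resume.*

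This resolves the inconclusive case on the cautious side, as Section 3.5.1 does, and states the resumption after a negative work-up that Table 2 only implies.

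Leave the dose on resumption to the existing rules in Sections 3.4 and 3.5.1. A specific bar on resuming for patients already at 20 mg should not be added: neither ILD text contains one, and it could remove a patient whose symptoms proved to have another cause.

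The cost is a wording addendum. The immediate stop on suspicion is kept, and no new assessment is needed because Section 3.5.1 already calls for the chest CT.

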3.6 Duration of Agent-specific treatment

In the absence of treatment delays due to adverse event(s), treatment may continue until one of the following criteria applies:

- Extraordinary Medical Circumstances: If at any time the constraints of this protocol are detrimental to the patient's health, protocol treatment should be discontinued. In this event submit forms according to the instructions in the MATCH Forms Packet.
- Patient withdraws consent.
- Patient experiences unacceptable toxicity.
- Non-protocol therapies are administered.
- Disease progression

3.7 Duration of Follow-Up

Refer to the MATCH Master Protocol for specifics on the duration of follow-up.

Rev.12/16

Rev. 3/17

Rev.2/16

4. Study Parameters

4.1 Therapeutic Parameters for Afatinib Treatment

NOTE: In addition to the study parameters listed in the MATCH Master Protocol, the below parameters must also be performed for patients receiving afatinib treatment.

NOTE: All assessments required prior to registration to treatment should be done \leq 4 weeks prior to registration to Steps 1, 3, 5, 7, excluding the radiologic evaluation and electrocardiogram (ECG).

Test/Assessment	Prior to Registration to Treatment	Treatment			End of Treatment	Follow Up ^F
		Cycle 1, day 8 and day 15 ^G	Every Cycle, prior to treatment	Every 2 Cycles		
H&P, Weight, Vital signs ^A	X		X ^J			X
Performance status	X	X	X ^J			X
CBC w/diff, plt ^B	X		X ^J			X
Serum chemistry ^B	X		X ^J			X
Radiologic evaluation ^D	X			X ^D		X ^F
β -HCG ^C	X					
Toxicity Assessment ^G		X	X		X	X ^F
Pill Count/Diary ^H			X		X	
ECG ^K	X		X ^I			
Echocardiogram or Nuclear Study ^K	X ^I		X ^I			X ^I
Tumor biopsy and blood sample for MATCH Master Protocol ^E				X	X	

^A. History and physical, including vital signs and weight at the start of each cycle (up to 3 days before start of new cycle).

^B. Albumin, alkaline phosphatase, total bilirubin, bicarbonate, BUN, calcium, creatinine, glucose, phosphorus, potassium, SGOT[AST], SGPT[ALT], sodium, magnesium and serum tumor markers (including LDH, PSA if appropriate). For eligibility purposes, participants with creatinine levels above institutional normal, Cockcroft-Gault will be used to calculate creatinine clearance. CBC w/diff, platelets and serum chemistries should be performed on cycle 1, day 1 (or up to 7 days prior), and at the start of each subsequent cycle (up to 3 days before start of new cycle). CBC with differential will be performed more frequently in patients with grade 4 neutropenia or thrombocytopenia until resolution to \leq grade 3. CBC and serum chemistries are only required in follow-up until values return to pre-treatment levels or until progressive disease.

^C. Blood pregnancy test (women of childbearing potential) required prior to beginning treatment.

^D. Disease measurements are repeated every 2 cycles for the first 26 cycles, and every 3 cycles thereafter until PD or start of another MATCH treatment step. The baseline evaluation should be performed as closely as possible to the beginning of treatment and never more than 6 weeks

before registration to treatment step. For multiple myeloma patients, please refer to Section 6.4 of the MATCH Master Protocol for additional information on myeloma response criteria and the required disease assessments. Documentation (radiologic) must be provided for patients removed from study for progressive disease.

Rev.Add13 E. Additional blood specimens and/or biopsies are to be submitted from consenting patients per Section 9.3.2 of the MATCH Master Protocol. Submit at the following time points, as applicable:

- Blood specimens are to be submitted at the end of Cycle 2 (prior to start of Cycle 3 treatment). If patient progresses or treatment is discontinued prior to Cycle 3, collect the blood at that time instead. On-treatment kits for blood sample collections will be automatically shipped to sites upon registration to the treatment step.
- Screening biopsies for additional aMOI assessments after registration to appropriate screening step, if applicable (Step 2 or Step 4).
- At end of all MATCH study treatments, blood specimens and/or research biopsy after consent and registration to Step 8

Please refer to Section 4 of the MATCH Master Protocol to determine whether the patient proceeds to the next screening step or to follow-up (with a potential end of treatment biopsy for research purposes on Step 8). Samples are to be submitted as outlined in Section 9 of the MATCH Master Protocol. To order Step 2/4 Screening or Step 8 kits, complete the EAY131 Collection and Shipping Kit Order Form (See Appendix XII of the MATCH Master Protocol) and fax to [contact].

Rev.2/16 F. Every 3 months if patient is < 2 years from study entry, and every 6 months for year 3. Toxicity assessments and radiologic evaluations are not required to be done during Follow Up if progression has been previously reported; however if an adverse event occurs post treatment that meets the SAE reporting requirements, it still must be reported via CTEP-AERS, even if progression has occurred.

G. Site personnel should evaluate for toxicity and discuss treatment compliance with the patient in order to ensure the medication is taken correctly. This evaluation may be conducted by telephone or in person. The Toxicity Assessment is not required prior to Cycle 1, but is required every subsequent cycle.

H. The pill calendar will be collected at the end of every cycle. The Pill Count/Diary is not required prior to Cycle 1, but is required every subsequent cycle.

I. As clinically indicated

J. For Cycle 1, if following tests/assessments occurred within 7 days of Day 1, they do not need to be repeated at this timepoint. H&P, Weight, Vital signs; Performance Status; CBC w/diff plts; Serum chemistry; Concomitant Medications.

Rev.2/16 K. Within 8 weeks of treatment assignment (or within 4 weeks prior to registration to treatment for ECHO/nuclear study if clinically indicated, per Section [2.1.4](#))

Rev. Add13 5. **Drug Formulation and Procurement**

This information has been prepared by the ECOG-ACRIN Pharmacy and Nursing Committees.

Availability

NO STARTER SUPPLIES MAY BE ORDERED. Subjects must be enrolled and assigned to the treatment subprotocol prior to submitting the clinical drug request to PMB.

Drug Ordering: NCI supplied agents may be requested by the eligible participating Investigators (or their authorized designee) at each participating institution.

Pharmaceutical Management Branch (PMB) policy requires that drug be shipped directly to the institution where the patient is to be treated. PMB does not permit the transfer of agents between institutions (unless prior approval from PMB is obtained – see general information) The CTEP-assigned protocol number must be used for ordering all CTEP-supplied investigational agents. The eligible participating investigators at each participating institution must be registered with CTEP, DCTD through an annual submission of FDA Form 1572 (Statement of Investigator), NCI Biosketch, Agent Shipment Form, and Financial Disclosure Form (FDF). If there are several participating investigators at one institution, CTEP-supplied investigational agents for the study should be ordered under the name of one lead investigator at that institution.

Submit agent requests through the PMB Online Agent Order Processing (OAOP) application (<https://ctepcore.nci.nih.gov/OAOP>). Access to OAOP requires the establishment of a CTEP Identity and Access Management (IAM) account (<https://ctepcore.nci.nih.gov/iam>) and the maintenance of an “active” account status, a “current” password, and an active person registration status.

NCI Supplied Agent(s) – General Information

Questions about drug orders, transfers, returns, or accountability should be addressed to the PMB by calling [contact] Monday through Friday between 8:30 AM and 4:30 PM Eastern Time or email [contact] anytime.

Drug Returns: All undispensed drug supplies should be returned to the PMB. When it is necessary to return study drug (e.g., sealed bottles remaining when PMB sends a stock recovery letter), investigators should return the study drug to the PMB using the NCI Return Agent Form available on the NCI home page (<http://ctep.cancer.gov>).

Rev. 12/16

Drug Accountability: The investigator, or a responsible party designated by the investigator, must maintain a careful record of the receipt, disposition, and return of agent received from the PMB using the NCI Investigational Agent Accountability Record Form for Oral Agents available on the NCI home page (<http://ctep.cancer.gov>). Maintain separate NCI Investigational Agent Accountability Records for each agent, strength, formulation and ordering investigator.

Rev. 3/17

Investigator Brochure Availability: The current versions of the IBs for PMB-supplied agents will be accessible to site investigators and research staff through the PMB Online Agent Order Processing (OAOP) application. Access to OAOP requires the establishment of a CTEP Identity and Access Management (IAM) account and the maintenance of an “active” account status, a “current” password, and active person registration status. Questions about IB access may be directed to the PMB IB coordinator at [contact]

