3.4.3 Dose reduction for afatinib

Intra-patient dose reduction by 1, and if needed 2, dose-levels will be allowed depending on the type and severity of toxicity encountered provided that criteria for patient withdrawal from study treatment have not been met. Intrapatient dose re-escalation is not allowed.

All intra-patient dose reductions are relative to the lowest dose level of the current cycle.

Recovery to acceptable levels of toxicity must occur within 2 weeks to allow continuation in the study.

No more than 2 dose reductions are permitted for any patient. If further dose reduction is required, the patient must be removed from the study.

The following table describes the recommended dose modifications for study treatment associated toxicity:

Table 2. Dose Modification for Afatinib

Toxicity	Grade 1	Grade 2	Grade 3	Grade 4
Non-hematologic Toxicity (except specific toxicities mentioned below) ^{a,b,c}	Continue at the same dose level.	Continue at the same dose level.	Withhold dose until toxicity is grade ≤ 1 or has returned to baseline. Then reduce the dose by 1 level and resume treatment.	Withhold dose until toxicity is grade ≤ 1 or has returned to baseline. Then reduce the dose by 1 level or discontinue treatment (discretion of the investigator).
Cardiac Toxicity	Continue at the same dose level.	Continue at the same dose level except for asymptomatic decrease of LVEF by an absolute value of 20% (or more) and to $<$ institutional LLN. Withhold dose until toxicity is grade ≤ 1 . Then reduce dose by 1 level and resume treatment.	Discontinue study treatment.	Discontinue study treatment.
Renal Toxicity	Continue at the same dose level.	Withhold dose until toxicity is grade ≤ 1 . Then reduce dose by 1 level and resume treatment.	Withhold dose until toxicity is grade ≤ 1 . Then reduce dose by 1 level and resume treatment.	Withhold dose until toxicity is grade ≤ 1 . Then reduce dose by 1 level and resume treatment or discontinue treatment (discretion of the investigator).
Diarrhea	Continue at the same dose level. ^b	Continue at the same dose level unless diarrhea persists for 2 or more days despite adequate anti-diarrheal medication or hydration. Withhold dose until toxicity is grade ≤ 1 . Then reduce dose by 1 level and resume treatment.	Withhold dose until toxicity is grade ≤ 1 . Then reduce dose by 1 level and resume treatment.	Withhold dose until toxicity is grade ≤ 1 . Then reduce dose by 1 level and resume treatment.

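### Do footnotes D and F of the study calendar set conflicting scan intervals for a patient who stops afatinib without progression?

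*Protocol*

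**What the plan says.** The calendar in Protocol Section 4.1 has one row for radiologic evaluation. The row label carries footnote D, the every-2-cycles treatment cell carries D, and the Follow Up cell carries F. The Follow Up column heading also carries F.

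Footnote D sets disease measurements "every 2 cycles for the first 26 cycles, and every 3 cycles thereafter until PD or start of another MATCH treatment step". The same footnote holds the baseline imaging window, the reference to myeloma response criteria and the rule on documenting progression.

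Footnote F times follow-up as "Every 3 months if patient is < 2 years from study entry, and every 6 months for year 3", and adds that "Toxicity assessments and radiologic evaluations are not required to be done during Follow Up if progression has been previously reported". A patient in follow-up without reported progression is therefore still scanned.

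Other sections describe stopping. Section 3.4: "If treatment is delayed beyond 2 weeks the subject will come off study for unacceptable toxicity". Section 3.4.3: "If further dose reduction is required, the patient must be removed from the study". Section 3.5, on interstitial lung disease: "Afatinib should not be restarted in those patients suspected of having drug-related ILD and the subject should be removed from the study". Section 3.6 lists "Patient experiences unacceptable toxicity" among the reasons to end treatment. Section 3.7 reads "Refer to the MATCH Master Protocol for specifics on the duration of follow-up".

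**The concern.** Footnote D does not end with afatinib. Progression is named separately, so its second end point, the start of another MATCH step, matters only for someone already off afatinib without progression. Footnote F covers that same person, because it waives scans only after progression. The intervals differ, no sentence ranks the footnotes, and Section 3.7 defers only the duration of follow-up to the Master Protocol.

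The wording on stopping seems to add to the doubt. Three sections speak of leaving the study, while Section 3.6 treats toxicity only as a reason to stop treatment.

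What would be at stake is the recorded date of progression. If sites follow F off drug, those patients are scanned less often and their progression is dated later. If sites differ, the interval also varies by site. Time to progression and duration of response would be affected; best response hardly at all.

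**Working it through.** **Inputs.** Cycle length of 28 days (Schema); intervals from footnotes D and F (Section 4.1). Assumption: one month = 365.25/12 days. The protocol gives no detection-delay figure to reproduce.

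**1. Intervals**

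| Period | D | F | F/D |
|---|---|---|---|
| Years 1-2 | 2 × 28 = 56 days | 365.25/4 = 91.3 days | 1.63 |
| Year 3 | 3 × 28 = 84 days | 365.25/2 = 182.6 days | 2.17 |

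D's change of interval falls at 26 × 28 = 728 days, or 1.99 years. It therefore lines up with F's two-year mark.

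**2. Detection delay.** If progression is equally likely at any time between scans, the mean delay is half the interval.

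- Years 1-2: 28.0 against 45.7 days, difference 17.7 days = 2.5 weeks. The longest possible delay differs by 91.3 − 56 = 35.3 days, about 5 weeks.
- Year 3: 42.0 against 91.3 days, difference 49.3 days = 7.0 weeks. The longest possible delay differs by 182.6 − 84 = 98.6 days, about 14 weeks. This concerns only patients past two years who are off afatinib, have not progressed and have started no other MATCH step.

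**3. Sensitivity.** For exponential progression with rate r = ln 2/median and scan interval T, the mean lag is T/(1 − exp(−rT)) − 1/r. With T = 8 weeks (D) and 13.04 weeks (F):

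- assumed median 8 weeks: 4.46 against 7.73 weeks, difference 3.3;
- assumed median 52 weeks: 4.07 against 6.71 weeks, difference 2.6.

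The years 1-2 figure is stable at roughly 2.5 to 3.3 weeks.

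**4. Scan counts.** From study entry to two years, D gives 728/56 = 13 scans and F gives 8. That comparison overstates the gap, because nobody is in follow-up from day 1. For an assumed stop at day 112, the scans left to two years are 11 under D and 6 or 7 under F, depending on whether F is counted from the stop or from study entry.

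**5. Effect on a whole-trial mean.** If a share s of patients progress after stopping in years 1-2, the mean recorded date moves by about s × 2.5 weeks, and so by less than 2.5 weeks for any s below 1. The document does not give s.

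**6. Which footnote governs, read from the table.**

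- The Follow Up cell carries F and not D. Superscripts on cells are how a calendar assigns its rules.
- D on the row label is explained by its other content: the baseline window, myeloma criteria and documentation rule apply to the row whatever the interval.
- The toxicity row is built the same way. Its label carries footnote G, which has a per-cycle rule, and its Follow Up cell carries F. Nobody would run G by cycle after treatment.
- D counts in cycles. Off drug there are none, so D could be applied only by inventing a calendar conversion that the text does not contain.
- Footnote E sends sites to Section 4 of the Master Protocol to decide whether a patient goes to the next screening step or to follow-up. Follow-up is thus a separate phase, and F times it.

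**The case for a change.** The strongest opposing case is that a column marker does not cancel an explicit end point. If F governs off drug, D's second end point has nothing to do; if D governs, the F tag is wrong. Patients who stop without progression are also expected, since the protocol takes them off for long holds, for needing a third dose reduction and for interstitial lung disease. Even if every site follows F, the scan interval depends on treatment status.

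Part of this stands. D's closing clause is loose, and no sentence says that D ends with treatment. The dependence on treatment status is real too. But it is what F prescribes: lighter imaging after treatment is a common and defensible choice. Holding patients to the denser schedule would cost about one more scan per 24 weeks in years 1-2 (168/56 = 3.0 against 168/91.3 = 1.8) and about two more in year 3 (4.3 against 2.0), for each patient who stops without progression. This is a one-treatment subprotocol, so the difference cannot distort a comparison between arms within it. It also states no time-to-event analysis of its own for the extra scans to serve.

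The point about leaving the study carries less weight. Section 3.4 also describes the consequence of a long interruption as removal from this subprotocol, and footnote F requires scans until progression is reported. The wording is loose but does not tell sites to stop observing.

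**Conclusion.** No change to the plan follows. The intervals do differ, but the calendar shows by column which one applies: D on treatment, F in follow-up. Sites and analysts would read it that way, and on that reading clarifying the clause alters no result. What remains is one imprecise end clause in footnote D.

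If some sites did carry D past treatment, the difference in detecting progression off drug would average about 2.5 weeks in years 1-2 (2.6 to 3.3 under the exponential check), and about 7 weeks in year 3 for the patients still without progression. These figures assume scans held on schedule. The first and last also assume progression spread evenly between scans. The effect on any whole-trial estimate cannot be computed, because the share stopping without progression is not given.

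The conclusion rests on the ordinary reading of the table. The Master Protocol is not at hand. Section 4.1 says its parameters add to those listed there, so the follow-up interval may already be settled in that document.
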